7.3 Adverse Events and Serious Adverse Events

In the present study, an adverse event and serious adverse event will be defined as follows:

An adverse event (AE) will be defined as any unfavorable and unintended diagnosis, symptom, sign (including an abnormal laboratory finding), syndrome or disease which either occurs during the study, having been absent at baseline, or if present at baseline, appears to worsen. Adverse events will be recorded regardless of their relationship to the study intervention.

A **serious adverse event (SAE)** will be defined as any untoward medical occurrence that results in death, is life threatening, requires inpatient hospitalization or prolongation of existing hospitalization, results in persistent or significant disability/incapacity, or is a congenital anomaly.

Since we do not anticipate any laboratory value changes due to the TARA study intervention, no laboratory values will be collected as part of the current protocol; thus, no laboratory values will be collected to assess safety.

Solicited adverse events will be captured in the following manner: (1) the Child Outcome Rating Scale (CORS) including the following question: "Has there been any significant unfavorable change in your mental or physical health since last class?" will be administered at every TARA session (please see Appendix. Not a source document.); (2) if the participant answers "no" to this question on the CORS, then no additional information will be requested; (3) if the participant answers "yes" to this question on the CORS and the reported event meets the definition of an adverse event given above, then the research assistant or another study staff member will ask the participant for additional details regarding the participant's answer to the CORS question and this information will be recorded in the Adverse Event form within 24 hours of the TARA study intervention session.

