In order to assure that the reporting and data collection systems avoid double capture of solicited and unsolicited events, we have implemented the following items in our protocol: (1) We will ask all of the participants to report any unsolicited events in the CORS after the question, "Has there been any significant unfavorable change in your mental or physical health since the last class?"; (2) If a participant reports an unsolicited event to any of the study staff, the study staff member will ask the participant to write down this information in the CORS in order to avoid double capture of the event; (3) We also will specifically instruct our research assistants and staff to not duplicate the recording (i.e., double capture) of the same solicited and unsolicited events; (4) At the weekly clinical trial research lab meetings, the PIs (Drs. [name] and [name]) will review with the research staff all of the CORS forms, AE and SAE forms for the prior week in order to ensure that there is no double capture(s) of any solicited and unsolicited event(s).

Time Period and Frequency for Event Assessment and Follow-Up

Unanticipated problems will be recorded in the data collection system throughout the study.

To satisfy the requirement for prompt reporting, unanticipated problems will be reported using the following timeline:

- Unanticipated problems that are serious adverse events will be reported to the IRB, Independent Safety Monitors, and NCCIH within 7 days of the investigator becoming aware of the event.
- Any other unanticipated problem will be reported to the IRB, Independent Safety Monitors, and NCCIH within 15 days of the investigator becoming aware of the problem.

All unanticipated problems will be reported to appropriate institutional officials (as required by an institution's written reporting procedures), the supporting agency head (or designee), and OHRP within one month of the IRB's receipt of the report of the problem from the investigator.

Adverse Event Reporting

SAEs that are unanticipated, serious, and possibly related to the study intervention will be reported to the Independent Safety Monitors, IRB, and NCCIH in accordance with requirements.

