7.4 Reporting Procedures

Please see below, Table A, for details of the reporting procedures and timelines, including the individual responsible for each step (e.g., the PIs, the Independent Monitors, etc.). The medical director, [name] (co-PI), will make the decision regarding determining the relatedness and severity of any and all AEs and SAEs. The appropriate AE and SAE forms will be completed. The completed AE and SAE forms will be sent and distributed to the appropriate individual or group of individuals (i.e.,

UCSF IRB, NCCIH) as stated below in Table A (please see below, Table A). The PIs will record all reportable events with start dates occurring any time after informed consent is obtained until 7 days (for non-serious AEs) or 30 days (for SAEs) after the last day of study participation. A research assistant will perform the duties of the Internal QA reviewer. At each study visit, the investigator will inquire about the occurrence of AE/SAEs since the last visit. Events will be *followed* for outcome information until resolution or stabilization.

Table A

Data type	Frequency of review	Reviewer
Subject accrual (including compliance with protocol	Monthly	PIs, Internal QA Reviewer
enrollment criteria)	Semi-annually	Independent Monitors
Status of all enrolled subjects, as	Monthly	PIs, Internal QA Reviewer
of date of reporting	Semi-annually	Independent Monitors
Data entry quality control checks on 100% of charts	Weekly	QA Reviewer
Adherence data regarding study	Monthly	PIs, Internal QA Reviewer
visits and intervention	Semi-annually	Independent Monitors
AEs and rates (including out-of-	Monthly	PIs, Internal QA Reviewer
range lab values)	Semi-annually	Independent Monitors
	Annually	NCCIH
SAEs (unexpected and related)	Per occurrence	PIs, Independent Monitors NIH/NCCIH
SAEs (expected or unrelated)	Per Occurrence	PIs, Internal QA Reviewer
	Annually	Independent Monitors, NIH/NCCIH
Unanticipated Problems	Monthly	PIs, Internal QA Reviewer
	Per Policy	IRB

Reporting Changes in Study Status

During the funding of this study, any action by an IRB, the Independent Monitors, or one of the study investigators that results in a temporary or permanent suspension of the study will be reported to the NCCIH Program Official within 3 business days of notification.

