10. DATA COLLECTION AND QUALITY ASSURANCE

10.1 Data Collection Forms

Information for each participant will be collected using the following forms and procedures:

- o Informed Consent Form (will be obtained and signed by RA via DocuSign)
- Medical History Form (source document, will be collected and signed by RA via DocuSign)
- o Inclusion/Exclusion criteria form (source document, will be filled out and signed by RA via DocuSign)
- Enrollment/Randomization form (source document, will be filled out and signed by RA via DocuSign)
- o MRI screening form (will be signed by the MRI technician. Not a source document.)
- o MRI brain scan (will be performed using a 3T MRI scanner)
- o Demographics assessment (will be performed electronically in Qualtrics)
- SDQ assessment (will be performed electronically in Qualtrics)
- Baseline Visit Checklist (source document, will be filled out and signed by RA via DocuSign)
- Child Session Rating Scale (CSRS) (source document, will be collected and signed by RA)
- Child Outcome Rating Scale (CORS) including the question: "Has there been any significant unfavorable change in your mental or physical health since last class?" (will be collected by RA. Not a source document.)
- o Adverse Events (source document, if the answer is Yes to the question above in CORS, this form will be filled out and signed by RA via DocuSign)
- Serious Adverse Events (source document, if answered Yes to the SAE question in the Adverse Event form, this form will be filled out by RA, signed by PI via DocuSign)
- o On Study Visit Checklist Form (source document, will be filled out and signed by RA via DocuSign)
- Study Completion form (source document, will be filled out by RA, signed by PI via DocuSign).

All source documents will be signed and stored electronically in DocuSign. Any data, forms, reports, video recordings, and other records that leave the site will be identified only by a participant identification number (Participant ID, PID) to maintain confidentiality. All computer entry and networking programs will be done

using PIDs only. Information will not be released without written permission of the participant, except as necessary for monitoring by the UCSF IRB, the NCCIH, and the OHRP.

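### The rules for recording adverse events conflict, and staff who follow the CORS route can miss or delay events that the under-15% safety criterion counts

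*Combined protocol and SAP*

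**What the plan says.** Section 7.3 of the combined protocol and SAP defines an adverse event broadly, as "any unfavorable and unintended diagnosis, symptom, sign (including an abnormal laboratory finding), syndrome or disease" that is new or worse since baseline, whatever its relation to the intervention.

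The screening question on the Child Outcome Rating Scale (CORS) is narrower: "Has there been any significant unfavorable change in your mental or physical health since last class". After a no, "then no additional information will be requested". After a yes, an event that meets the definition goes on the AE form within 24 hours of the session.

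The same section then lists four measures to "assure that the reporting and data collection systems avoid double capture of solicited and unsolicited events". Item (1) invites participants to add unsolicited events after the question. Under item (2), if a participant reports an event to staff, "the study staff member will ask the participant to write down this information in the CORS". Item (4) is a weekly meeting at which the principal investigators "will review with the research staff all of the CORS forms, AE and SAE forms for the prior week", again to exclude duplicates.

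Sections 6.2.4, 6.2.5 and 10.1 list the AE form as conditional on a yes to the CORS question. Section 10.1 says of the CORS itself: "will be collected by RA. Not a source document".

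Other sections are wider. Section 7.4, repeated in 7.5, states: "At each study visit, the investigator will inquire about the occurrence of AE/SAEs since the last visit". Section 7.2 sends all adverse events at the TARA visits to the AE form, Section 7 says an event that occurs is recorded there, and 6.2.1 has the form completed when a participant reports an event.

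**The concern.** Item (2) deals with an event that a staff member already knows about. Instead of telling that person to record it, the text hands the task back to the adolescent, on a form tied to class sessions. Sections 5.1 and 7 tell participants with difficult emotions or restlessness, the reactions the protocol expects, to speak to the class leader or study staff. So the oral route is the one the expected reactions are likely to take.

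Two results depend on what reaches the AE form. One is the criterion in 7.1 and 9.5.2 that fewer than 15% of participants have a related grade 2 or 3 event. The other is the 15% safety-review trigger in 9.4. Incomplete capture can only lower these counts.

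**Working it through.** The 15% threshold has no derivation in the documents, so there is no planned figure to reproduce. The check has three parts: the rules set side by side, the counts behind the threshold, and an illustration.

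**1. What each set of rules does with the same event**

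| Situation | CORS route (6.2.4, 6.2.5, 7.3, 10.1) | Wider rules (6.2.1, 7, 7.2, 7.4, 7.5) |
|---|---|---|
| Told to staff; participant attends, answers yes and writes it down | AE form | AE form |
| Told to staff; participant writes it on the CORS but answers no | No rule opens an AE form and nobody is named to transfer the entry | AE form |
| Told to staff; participant then misses class or is temporarily off the intervention | No CORS until return (Section 8 suspends evaluations meanwhile); delayed, or unrecorded if never written | Section 7 calls for an AE form; the 7.4 inquiry comes only at the next visit |
| Not mentioned; participant does not regard it as *significant* | Inquiry ends at no | Investigator asks (7.4) |

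The two routes agree only in the first row. The list for Visits 2 to 13 in 6.2.4 has no separate item for the investigator's inquiry. The weekly review cannot find an event that reached no form, and looking for missed events is not its stated purpose.

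**2. Counts behind the threshold**

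Arm sizes are 50 TARA and 50 waitlist (9.1). Section 7.1 speaks of participants and 9.4 of enrolled participants, so the denominator is not settled.

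- Denominator 50: 0.15 × 50 = 7.5. Seven (14%) pass and eight (16%) fail.
- Denominator 100: 0.15 × 100 = 15. Fourteen pass and fifteen fail.

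Under either reading, a count at the boundary changes sides if one affected participant is missed.

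**3. Illustration under assumed rates**

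The documents give neither an expected event rate nor a capture rate. Let p be the true share of TARA participants with a related grade 2 or 3 event. Let L be the share of those participants whose qualifying events are all missed. With denominator 50, P(criterion met) = P(X ≤ 7), where X ~ Binomial(50, p(1 − L)).

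| Assumed p | L = 0 | L = 10% | L = 25% | L = 50% |
|---|---|---|---|---|
| 10% | 0.878 | 0.923 | 0.968 | 0.997 |
| 15% | 0.519 | 0.639 | 0.805 | 0.968 |
| 20% | 0.190 | 0.300 | 0.519 | 0.878 |
| 30% | 0.007 | 0.023 | 0.098 | 0.519 |

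With denominator 100, and related events assumed to arise only among the 50 trained, the bound is X ≤ 14. At p = 20% the chances are 0.939, 0.973, 0.995 and 1.000 for the same four losses. At p = 30% they are 0.447, 0.633, 0.864 and 0.995.

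The tables show the direction and how sensitive the criterion is. They do not estimate the loss in this trial, which may be zero.

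**The case against.** The strongest reply is that the protocol already calls for full capture. Sections 6.2.1, 7, 7.2, 7.4 and 7.5 do not depend on the CORS answer, and the recording window runs to 7 days (AEs) or 30 days (SAEs) after participation. Item (2) does not forbid an AE form. Item (1) invites any unsolicited event without the word *significant*. The CORS is also given at Visit 14, including to those who stop the intervention early, so a missed class may mean delay and not loss. All of this stands. A reader might infer that events are certain to be lost and that the count will be too low; the documents do not support that. They show two incompatible instructions and a missing transfer rule.

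The *significant* filter would mainly drop mild events, which lie outside the criterion. That also stands. The stronger limb is item (2), because a moderate event already known to staff may get no AE form.

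A reader might also infer that the Fisher comparison of grade 2 or higher events in 9.6 is biased in favor of TARA. That does not follow. CORS collection is tied to TARA sessions, and none is stated for the waitlist arm before Visit 14, so closer questioning in the TARA arm could push the comparison the other way.

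Nor does the CORS need to become a source document. The AE form already is one, and it is enough that events reach it.

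**Conclusion.** The point holds as a conflict between capture rules, with a risk of under-counting. Staff who follow 6.2.4, 6.2.5, 7.3 and 10.1 as written can miss or delay events that 7.2 and 7.4 require to be recorded, including moderate related ones. The under-15% result and the safety-review trigger may then be biased low. The size cannot be derived from the documents and would be nil if staff followed the wider rules throughout. The statement that one participant can change the result rests on a count at the boundary: 7 against 8 if the denominator is the 50 in TARA, 14 against 15 if it is all 100. The probabilities above rest on assumed event and loss rates. The primary analysis of putamen node strength is not affected.

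**What to change.** Replace item (2) of the list in Section 7.3 with:

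> Any event reported to any staff member, or written on the CORS whatever the answer to the question, is entered by staff on the AE form within 24 hours. Duplicates are reconciled at the weekly review by PID and onset date, and that review also checks for events without an AE form.

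The 24-hour interval is the one 7.3 already uses after a yes. Then align 6.2.4, 6.2.5, the stop-at-no step in 7.3, and 10.1 with 7.2 and 7.4, so that the AE form no longer depends on the CORS answer. Drop *significant* from the CORS question so that it matches the AE definition.

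The cost is wording in four sections and one question on a form, a few more mild events on file, and some duplicates to reconcile at a meeting that already takes place. No new visits or staff are needed. If enrollment has begun, note the date of the change, because capture before and after it may differ.

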7.4 Reporting Procedures

Please see below, Table A, for details of the reporting procedures and timelines, including the individual responsible for each step (e.g., the PIs, the Independent Monitors, etc.). The medical director, [name] (co-PI), will make the decision regarding determining the relatedness and severity of any and all AEs and SAEs. The appropriate AE and SAE forms will be completed. The completed AE and SAE forms will be sent and distributed to the appropriate individual or group of individuals (i.e.,

UCSF IRB, NCCIH) as stated below in Table A (please see below, Table A). The PIs will record all reportable events with start dates occurring any time after informed consent is obtained until 7 days (for non-serious AEs) or 30 days (for SAEs) after the last day of study participation. A research assistant will perform the duties of the Internal QA reviewer. At each study visit, the investigator will inquire about the occurrence of AE/SAEs since the last visit. Events will be *followed* for outcome information until resolution or stabilization.

Table A

Data type	Frequency of review	Reviewer
Subject accrual (including compliance with protocol	Monthly	PIs, Internal QA Reviewer
enrollment criteria)	Semi-annually	Independent Monitors
Status of all enrolled subjects, as	Monthly	PIs, Internal QA Reviewer
of date of reporting	Semi-annually	Independent Monitors
Data entry quality control checks on 100% of charts	Weekly	QA Reviewer
Adherence data regarding study	Monthly	PIs, Internal QA Reviewer
visits and intervention	Semi-annually	Independent Monitors
AEs and rates (including out-of-	Monthly	PIs, Internal QA Reviewer
range lab values)	Semi-annually	Independent Monitors
	Annually	NCCIH
SAEs (unexpected and related)	Per occurrence	PIs, Independent Monitors NIH/NCCIH
SAEs (expected or unrelated)	Per Occurrence	PIs, Internal QA Reviewer
	Annually	Independent Monitors, NIH/NCCIH
Unanticipated Problems	Monthly	PIs, Internal QA Reviewer
	Per Policy	IRB

Reporting Changes in Study Status

During the funding of this study, any action by an IRB, the Independent Monitors, or one of the study investigators that results in a temporary or permanent suspension of the study will be reported to the NCCIH Program Official within 3 business days of notification.

7.5 Followup for Adverse Events

The PIs will record all reportable events with start dates occurring any time after informed consent is obtained until 7 days (for non-serious AEs) or 30 days (for SAEs) after the last day of study participation. At each study visit, the investigator will inquire about the occurrence of AE/SAEs since the last visit. Events will be followed for outcome information until resolution or stabilization. In the cases of adolescents with severe depression or adolescents expressing passive suicidal ideation (i.e., the adolescent expresses some potential thoughts of self-harm, but there is no intent or plan to harm herself/himself), study participants with commercial or private health insurance plans will be referred to the UCSF Langley Porter Psychiatric Institute where [name] (co-PI) sees patients, and study participants without commercial or private insurance will be referred to the UCSF Zuckerberg San Francisco General Hospital which cares for all patients regardless of their ability to pay. Participants expressing imminent suicidal ideation will be placed on an involuntary 5150 72-hour hold for danger to self by [name]. [name] is a double board certified adult as well as child and adolescent psychiatrist who sees patients at UCSF, and he is legally authorized to place an involuntary 5150 72-hour hold on the adolescent for danger to self (i.e., suicidal ideation) in order to hospitalize the adolescent if needed. The UCSF Emergency Room (ER) is located immediately adjacent to the UCSF Langley Porter Psychiatric Institute where [name] personal clinical office and research lab are located. Following the established written protocols that are currently in place for any adolescent who expresses imminent suicidal ideation, [name] would evaluate and place an involuntary 5150 72-hour hold for danger to self on the suicidal adolescent. [name] would then contact the UCSF Langley Porter Psychiatric Institute security who are present in the building throughout the entire day and evening to help escort the suicidal adolescent to the UCSF ER. The ER physician in consultation with the on call child and adolescent psychiatrist would then evaluate the patient in the ER and decide whether to hospitalize the patient for the adolescent's safety and well-being.

7.6 Safety Monitoring

The Independent Monitoring Committee (IMC) for this study is comprised of Drs. [name], [name], and [name]. Drs. [name], [name], and [name] are not associated with this research project and work independently of the PIs, Drs. [name] and [name]. They are not part of the key personnel involved in this grant. No member of the Committee has collaborated or co-published with the PIs within the past three years. They are qualified to review the patient safety data generated by this study because of their unique expertise. Specifically, [name], a full Professor and a Board-Certified Child and Adolescent Psychiatrist, has devoted his career to the care and research of adolescents. [name] has exceptional expertise and extensive experience with clinical trial studies in children and adolescents. He has served on three IMCs. [name] is a Professor of Pediatrics who specializes in integrative medicine and behavioral health. [name] holds a PhD in medical statistics, and he has significant and extensive experience in clinical trials. (Please see the DSMP for the CVs of all members of the IMC).

8. INTERVENTION DISCONTINUATION

Participants who have met inclusion/exclusion criteria and been enrolled into the study may be discontinued if they no longer meet the study's inclusion and exclusion criteria (e.g., if the patient has started participation in another mindfulness-based intervention such as mindfulness-based stress reduction after they have enrolled into the TARA study intervention). The PIs (Drs. [name] and [name]) will determine when criteria are met (i.e., the participant no longer meets the study's stated inclusion and exclusion criteria) for discontinuing intervention for a participant.

Possible reasons for discontinuation of the study intervention include closure by the institute (i.e., UCSF) due to significant concerns over the continued safety of the participants such as the occurrence of a natural disaster (e.g., earthquake) that renders the buildings at UCSF where the TARA study intervention is being delivered unsafe due to structural building damage arising from the earthquake.

If the TARA study intervention is discontinued for a participant (i.e., the participant no longer meets the original study entrance inclusion and exclusion criteria), the participant will be followed for one additional visit in order to allow for all of the final visit (Visit 14) assessments to be performed. Once the final visit (Visit 14) assessments are completed, the participant will no longer continue to be followed except to follow any AEs or SAEs as stated above in Section 7.4 (i.e., until 7 days [for non-serious AEs] or 30 days [for SAEs] after the last day of study participation).

A participant who has been enrolled into the study may temporary discontinue treatment if the reason for discontinuation (e.g., cold) does not preclude the participant from successfully completing the remaining study visits without missing greater than 25 percent of the 12 total TARA intervention sessions (i.e., the participant must be able to attend and complete at least 75 percent of the 12 total TARA intervention sessions) within the timeframe specified in this study (please see above, Section 6.1, Schedule of Evaluations).

While an enrolled participant is temporarily discontinued from the study intervention (e.g., cold), no additional evaluations will be performed until the participant resumes with participating in the study intervention. Once the participant resumes with participating in the study intervention, the evaluations as specified above (please see Section 6.1, Schedule of Evaluations) will then be performed based upon which session number the participant resumes her/his participation in the study.

If an enrolled participant is permanently discontinued from study intervention, then the participant will be followed for one additional visit in order to allow for all of the final visit (Visit 14) assessments to be performed. Once the final visit (Visit 14) assessments are completed, the participant will no longer continue to be followed except to follow any AEs or SAEs as stated above in Section 7.4 (i.e., until 7 days [for non-serious AEs] or 30 days [for SAEs] after the last day of study participation).

